Patients will be randomized in a ratio of 2:1 to receive either pegcetacoplan or placebo, respectively. The randomization will be stratified by transfusion history (number of transfusions during the 6-month period prior to randomization \geq 1; 0). Every effort should be made to enroll patients in both subgroups.

The planned length of participation in the study for each patient is a maximum of 110 weeks. This study will consist of 5 periods:

- Screening period: up to 4 weeks (may be extended by up to 2 additional weeks).
- Double-blind treatment period: 24 weeks (Part A).
- Open-label treatment period: 24 weeks (Part B).
- Open-label maintenance period: up to additional 48 weeks or until the product becomes commercially available (Part C).
- Follow-up period: 8 weeks.

Screening period (up to 4 weeks; may be extended by up to 2 additional weeks)

Informed consent will be obtained during a screening visit prior to any study-related procedures being conducted. Patients experiencing acute hemolytic crisis may receive blood cell transfusions during the screening period. The start of dosing must occur at least 7 days after receiving last transfusion.

Patients will be screened to confirm that the patient selection criteria for the study have been met. Key inclusion and exclusion criteria will be reviewed by the study medical monitor and eligibility will be confirmed prior to the enrollment. If needed and after consultation with the medical monitor, the screening period may be extended by up to 2 additional weeks (e.g., eligibility laboratory results not available due to technical reasons or the patient receives an RBC transfusion during the last week of the screening period, reasonably reversible medical reasons such as COVID-19 infection).

Double-blind treatment period (24 weeks): Part A

A total of 57 patients who meet all of the inclusion criteria and none of the exclusion criteria will be randomized in a 2:1 ratio to either pegcetacoplan or placebo. Safety and efficacy will be assessed.

Patients randomized into the study will receive s.c. IMP (pegcetacoplan or placebo) twice weekly for 24 weeks.

All standard-of-care medications can be continued, with the exception of protocol-defined prohibited medications.

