6.4 Treatments

6.4.1 Treatments administered

6.4.1.1 Investigational medicinal products

Table 3 Investigational medicinal products

Investigational product	Dosage form	Route	Dose	Dosage regimen
Pegcetacoplan	Sterile solution in stoppered glass vials	Subcutaneous	1080 mg	Twice weekly
Placebo	Sterile solution in stoppered glass vials	Subcutaneous	Not applicable	Twice weekly

The pegcetacoplan treatment group will receive a dosage of 1080 mg twice weekly via s.c. infusion (20 mL) during the double-blind treatment period (24 weeks).

The placebo group will receive placebo s.c. infusion twice weekly during the double-blind treatment period.

Following the double-blind treatment period, patients from both treatment groups may enter the open-label treatment period (24 weeks) and will receive pegcetacoplan 1080 mg twice weekly via s.c. infusion (20 mL) (equivalent to 308 mg/day).

The open-label treatment period will be followed by an open-label maintenance period (maximum of additional 48 weeks or until the product becomes commercially available, whichever occurs first), and patients who benefited from therapy without significant side effects during the double-blind treatment period will continue receiving pegcetacoplan 1080 mg twice weekly via s.c. infusion (20 mL).

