8.3.1 General statistical issues

All statistical tests will be 2-sided and performed at a significance level of 5 % unless otherwise stated.

For all endpoints, Baseline will be the last assessment prior to the start of IMP treatment.

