## 5.2 KEY DEFINITIONS AND CONVENTIONS

### 5.2.1 Baseline values

The baseline value for any parameter will be defined as the last measurement prior to dosing on Day 1 of Part A of the study. If there are both central and local laboratory results available from samples collected at the same date and time, the central laboratory result will be selected for baseline. Baseline values can be obtained during screening or at visit 2 (before first dose). For ePRO questionnaires (FACT-An, SF-12, and EQ-5D-5L), baseline is collected prior to dosing but there are no times collected. When these assessments are performed on the date of first dose, the assessment will be considered as pre-dose for identification of a baseline.

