## 7.4 SECONDARY EFFICACY ENDPOINT ANALYSIS FOR PART B

All Part B secondary efficacy analyses will be analyzed with the ITT set, and data presentations will be by visit and by randomized treatment group in Part A as well as combined.

The change from Baseline at Week 48 in Hb, LDH, haptoglobin level, indirect bilirubin, ARC and D-dimer will be analyzed using descriptive statistics.

For the endpoint regarding the normalization of markers of hemolysis (LDH, indirect bilirubin and ARC) at Week 48, the number and percentage of patients who respond will be tabulated in frequency tables by randomized treatment group in Part A as well as combined. All data will be used as collected (no ICEs will be considered) and no imputations will be done.

Durability of response is the time until response is lost; response is lost at the first time point when the average change from baseline in Hb is < 1.5 g/dL (the average of all time points starting from Week 24), or the patient receives a transfusion, or the patient discontinues treatment or the study or the patient receives prohibited medication. Durability of response will be analyzed as a time to event variable with Kaplan-Meier statistics provided. Only patients randomized to pegcetacoplan in Part A who achieved the primary endpoint at Week 24 will be included in this analysis. The time to event will be defined as the time the patient achieved the primary endpoint at Week 24 until the earliest time durability of response (as defined above) is lost. Due to the termination of the study, durability of response will not be included in the analysis.

The change from Baseline at Week 48 in FACT-An, SF-12, EQ-5D-5L and FACIT-F subscale score of the FACT-An scale will be analyzed using descriptive statistics.

All data will be used as collected (no ICEs will be considered) and no imputations will be done.

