## 7.6 SAFETY ENDPOINT ANALYSIS

All safety analyses will be carried out descriptively on the safety set and presented by randomization sequence. For each output summary, all data will be presented as it becomes available. For example, data for Part A will be presented when Part A is reported. When Part B data are available, all cumulative data from Parts A and B will be reported together. When Part C data are available, all cumulative data from Parts A, B, and C will be reported.

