### 7.6.5 Immunogenicity data

Frequency tables will be presented to summarize the presence of anti-drug antibodies (ADA) to polyethylene glycol and to pegcetacoplan peptide. ADA evaluable patients are defined as:

- For baseline ADA: having at least one evaluable ADA sample at baseline.
- For treatment-emergent ADA and treatment-boosted ADA: having at least one evaluable ADA sample at baseline and at least one evaluable post dose sample.

Baseline ADA prevalence is defined as the number of patients with ADA positive at baseline divided by the number of patients with evaluable ADA at baseline.

Post-baseline ADA incidence is defined as the proportion of patients developing treatment-emergent ADA among those negative for ADA at baseline, or treatment-boosted ADA, among those positive for ADA at baseline.

Treatment-emergent ADA is defined as ADA that are present at a post-dose visit in a patient who had negative ADA at baseline.

Transient treatment-emergent ADA is defined as treatment emergent ADA detected in a single post dose sample (that was not the last assessment) or in more than 1 ADA sample where the first post dose and last ADA positive samples were separated by a period of less than 112 days (16 weeks), irrespective of any negative and positive samples in between. Persistent treatment emergent ADA is defined as more than 1 positive post dose ADA sample  $\geq 112$  days (16 weeks) apart or a positive ADA sample at the last time point with no further results available.

Treatment-emergent ADA can only be defined if baseline ADA result is obtained.

Treatment-boosted ADA is defined as positive ADA at a titer more than 4-fold the baseline titer found in a patient with positive ADA at baseline. Treatment-boosted ADA can only be defined if baseline ADA titer result is obtained.

Testing for neutralizing antibodies will be performed for all samples with positive ADA. Definitions for baseline Nab prevalence, post-baseline Nab incidence, and treatment-emergent Nab are the same as for ADA but with Nab.

A summary table of baseline ADA prevalence, post-baseline ADA incidence, treatment-emergent/boosted ADA, maximum titers for patients with treatment-emergent/boosted ADA,

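### Placebo-randomized patients keep their Day 1 baseline after starting pegcetacoplan at Week 24, so the open-label summaries give them no drug-only change and antibodies found on placebo count as treatment-emergent in their sequence

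*SAP*

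**What the plan says.** SAP 5.2.1 defines the baseline of any parameter as "defined as the last measurement prior to dosing on Day 1 of Part A of the study". Protocol 8.3.1 agrees: "For all endpoints, Baseline will be the last assessment prior to the start of IMP treatment". The term IMP covers both products (Protocol, Synopsis: "Patients randomized into the study will receive s.c. IMP (pegcetacoplan or placebo) twice weekly for 24 weeks"), so in the placebo arm the start of IMP is the first placebo dose. After Part A, "patients from both treatment groups may enter the open-label treatment period (24 weeks) and will receive pegcetacoplan" (Protocol 6.4.1.1). Neither document defines another baseline at that switch, or a time axis that starts at the first pegcetacoplan dose.

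For Part B efficacy, SAP 7.4 states: "The change from Baseline at Week 48 in Hb, LDH, haptoglobin level, indirect bilirubin, ARC and D-dimer will be analyzed using descriptive statistics". Its layout rule is that "data presentations will be by visit and by randomized treatment group in Part A as well as combined", and SAP 7.5 uses the same rule for Part C.

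Safety, which includes immunogenicity, follows another rule: "All safety analyses will be carried out descriptively on the safety set and presented by randomization sequence" (SAP 7.6). Data from Parts A, B and C are reported cumulatively as they become available. SAP 7.6.5 adds: "Treatment-emergent ADA is defined as ADA that are present at a post-dose visit in a patient who had negative ADA at baseline". It does not say which product the dose must be.

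SAP 1.1 records that enrollment was stopped early. Part B and C visits go into one descriptive table, and normalization and durability are not analyzed after Part A.

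**The concern.** Two stated objectives are to describe the long-term effect of pegcetacoplan and to assess its immunogenicity. For patients randomized to pegcetacoplan, study week equals time on drug, so a change from Day 1 serves the first objective directly. For patients randomized to placebo, a change from Day 1 to Week 48 is 24 weeks of placebo followed by 24 weeks of drug. Their own before-and-after change on pegcetacoplan is not tabulated, although it is a second, independent description of the effect in one third of the planned patients. A combined column by study week then averages patients at different durations of exposure.

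The antibody issue arises separately, from wording. A placebo patient who is negative on Day 1 and positive at Week 12 has had post-dose samples but no pegcetacoplan. Read literally, SAP 7.6.5 calls that a treatment-emergent antibody, and cumulative reporting of Parts A and B places it beside antibodies that appeared after real exposure.

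**Working it through.** The documents give no figure for this point. The one planned number needed is the size of the placebo arm.

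1. **Planned switchers.** The plan needs 54 evaluable patients and allows 5% non-evaluable: 54 / 0.95 = 56.8, so 57, as stated. At 2:1 this is 38 pegcetacoplan and 19 placebo; 19 / 57 = 33%.

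2. **Time on drug in a combined row at study week w ≥ 24.** Pegcetacoplan-randomized patients have w weeks and switchers have w − 24. With full enrollment and no dropout, the mean is (38w + 19(w − 24)) / 57 = w − 8.

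| Study week | Pegcetacoplan arm | Placebo arm | Combined mean |
|---|---|---|---|
| 32 | 32 | 8 | 24 |
| 48 | 48 | 24 | 40 |
| 96 | 96 | 72 | 88 |

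3. **Placebo-period change carried forward.** Let d be the mean change from Day 1 to Week 24 on placebo. It enters the placebo-arm column in full and the combined column as d × 19/57 = d/3. The documents give no d. For an assumed d of −1.0 to +1.0 g/dL Hb, the combined mean moves by −0.33 to +0.33 g/dL; at d = 0 it does not move.

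4. **What the by-arm column can recover.** The placebo-arm Week 48 mean minus its Week 24 mean equals the mean drug-period change only if the same patients contribute to both rows. The spread cannot be recovered: the variance of (Week 48 − Week 24) is Var48 + Var24 − 2·Cov, and the covariance is not tabulated. The median and quartiles of within-patient change are also unavailable.

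5. **Antibody samples before any pegcetacoplan.** Protocol Table 1 schedules ADA sampling on Day 1 and at Weeks 2, 4, 8, 12 and 24. In the placebo arm all five post-dose samples precede pegcetacoplan, because blood is drawn before dosing when IMP is given at the visit. If each sample had an independent probability f of testing positive, the chance of at least one positive is 1 − (1 − f)^5. An assumed f of 0.5% gives 2.5%, or 0.5 of 19 patients; f of 5% gives 22.6%, or 4.3 of 19. Positives at Weeks 2 and 24 (Days 15 and 169) are 154 days apart and would meet the 112-day rule for persistent ADA. The documents state no rate, so this range is illustrative.

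6. **Whether visits align by time on drug.** Switchers' study Weeks 32, 40, 48, 56, 64, 72, 80, 88 and 96 are drug Weeks 8, 16, 24, 32, 40, 48, 56, 64 and 72. Hematology, chemistry and FACT-An are scheduled at all of these weeks in the other arm. ADA sampling is not: the pegcetacoplan arm has none at Week 16, and switchers have none at drug Weeks 2, 4 or 12.

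7. **Effect of early termination.** From 10 January 2024 (end of enrollment) to 10 July 2024 (last date for treatment) is 182 days, or 26 weeks. A patient first dosed on the enrollment stop date could reach about Week 26, which for a switcher is about 2 weeks of drug. Week 48 (Day 337) requires a first dose by about 9 August 2023, and Week 96 (Day 673) by about 7 September 2022.

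**The case against.** The strongest reply is that nothing here contradicts the protocol. The Day 1 baseline follows Protocol 8.3.1, and the Week 48 and Week 96 endpoints are defined as change from that baseline. The Part B and C summaries carry no test. The pegcetacoplan-randomized column already describes long-term effect by true time on drug, and under SAP 1.1 the placebo arm's Week 24 and Week 48 rows should stand in the same table. All of this stands. It makes the matter an omission in a descriptive display, not an error. It does not supply the within-patient drug-only change for switchers.

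A reader might infer that the combined columns also pool antibodies. They do not: that column is specified only for efficacy, and immunogenicity is shown by randomization sequence. SAP 7.6.5 also provides time to onset, individual titer plots and a full listing, so an early positive could be traced by hand. The summary count would still include it, and the SAP does not say from which dose time to onset runs in a switcher.

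A reader might also infer that the SAP presents the combined change as a pegcetacoplan effect. It never says so; it reports change from Baseline as collected.

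Finally, the planned 19 of 57 will not be reached, and SAP 1.1 does not say whether the combined column survives in the single table. Both are correct and limit the size of the point.

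**Conclusion.** The point holds as a worthwhile, low-cost improvement to the open-label and immunogenicity summaries. For placebo-randomized patients, change from Baseline in Parts B and C includes 24 weeks on placebo, and no drug-only change is planned. Any combined efficacy row mixes exposures 24 weeks apart; the means of 40 weeks at Week 48 and 24 at Week 32 assume 2:1 allocation, full enrollment and no dropout. The Hb shift of d/3 shows direction and scale only. On antibodies, the defect is that the dose in post-dose is not specified; under cumulative reporting, the result is mixing within the placebo-to-pegcetacoplan sequence.

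The Part A primary and key secondary comparisons are unaffected. Durability was to use only the pegcetacoplan arm and, like later normalization, is no longer analyzed.

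**What to change.** Keep the Day 1 baseline for Part A and for the endpoints as defined. Then add the following for Parts B and C.

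- **Second baseline.** For placebo-randomized patients, derive a pegcetacoplan baseline: the last value before the first pegcetacoplan dose, normally the scheduled Week 24 pre-dose sample. SAP 5.2.3 already distinguishes Week 24 assessments made before open-label dosing. Questionnaires have no recorded time, so extend the SAP 5.2.1 convention (same-day assessment taken as pre-dose) to this switch.
- **Time on drug.** Present any combined efficacy summary by weeks on pegcetacoplan. Hematology, chemistry and FACT-An visits align. State in the SAP whether a combined column is kept under the reduced scope of SAP 1.1.
- **ADA.** In the placebo-to-pegcetacoplan sequence, report the placebo period separately from the period after the first pegcetacoplan dose. For the latter, take the pre-pegcetacoplan sample as baseline for treatment-emergent and boosted ADA, and run time to onset from that dose. Do not claim that ADA visits align across arms.

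The cost is two derived variables (a baseline flag and time since first pegcetacoplan dose) and slightly longer tables. No new sampling is needed.

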### 5.2.2 Missing data

In general, missing values will not be imputed for the analysis unless otherwise stated in the SAP or dataset specifications. Missing dates will not be imputed. However, if there is a missing start date for an AE, the AE will be considered treatment emergent. For concomitant medications (CM), the CM will be regarded as concomitant if the start date is missing. In the case of missing end dates for AEs and CMs, the events will be considered as ongoing at study end/end of Parts A, B, or C.

### 5.2.3 Visit Windowing

Data will be summarized and analyzed based on the list of visits specified in table below. The relative day of each assessment  $[(\text{date of assessment}) - (\text{date of first dose}) + 1]$  will be calculated for post randomization while the relative day of each assessment will be calculated as  $[(\text{date of assessment}) - (\text{date of first dose})]$  for prior to dosing. The relative day will be used to assign analysis visits following the table below.

Planned or nominal visits as recorded in the eCRF data will be considered first. Only if there is no planned visit or nominal visit recorded in the eCRF (or a planned visit contains missing data) unscheduled visits will be considered. Early termination visits will be treated like unscheduled visits and assigned to scheduled visits based on windows.

If more than 1 record is within the same analysis visit window, the record closest to the target day (the day of the planned visit according to protocol schedule of assessments) will be used in the analysis. If 2 records are tied for being closest to the target day, the earlier record will be used in the analysis. If there are both central and local laboratory results available from samples collected at the same date and time, the central laboratory result will be selected for the visit. If more than one assessment falls within the same defined window, the assessment closest to the target day with non-missing data will be considered for analysis.

If no planned, unscheduled, or early termination visit is within the analysis window the data for the visit will remain as missing.

**NOTE: Visits can only be assigned within periods.** A visit in the double-blind treatment period (Part A) can only be assigned to Part A and a visit in the open-label treatment period (Part B) can never be assigned to Part A. However, visits in Part B can be mapped to Part C and visits in Part C can be mapped to Part B as these periods are both open label. Since Week 24 visit is both the end of Part A and the start of dosing in Part B, assessments prior to OLE dosing at the Week 24 visit will be mapped to Part A. Assessments after the start of dosing during OLE will be mapped to Part B.

Period	Visit	Target Day	Analysis Window	Interval
Screening	Screening	-28 -- 1	< 1	NA
Double-blind treatment period (Part A)	Day 1	1	1	1
	Week 1	8	2–11	10
	Week 2	15	12–21	10
	Week 4	29	22* – 43	22
	Week 8	57	44 – 71	28
	Week 12	85	72 – 99	28
	Week 16	113	100 – 127	28
	Week 20	141	128 – 155	28
	Week 24	169	156 - 197	42
Open label treatment period (Part B)	Week 32	225	198 - 253	84
	Week 40	281	254 - 309	84
	Week 48	337	310 - 365	84
Open label maintenance period (Part C)	Week 56	393	366 - 421	84
	Week 64	449	422 - 477	84
	Week 72	505	478 - 533	84
	Week 80	561	534 - 589	84
	Week 88	617	590 - 645	84
EOT	Week 96	673	N/A	N/A
EOS	Week 104	729	N/A	N/A
	* Manually adjusted to allow +/- 7 at Week 4 visit as allowed in protocol			

## 6 STUDY SUMMARIES

### 6.1 DISPOSITION OF PATIENTS

Summary statistics will tabulate the number and percentage of patients who are screened, screen failures, randomized, received at least 1 dose of study treatment, who completed the study, who prematurely discontinued the study treatment along with associated reasons and who prematurely terminated the study along with associated reasons. This table will also show the number of patients who completed and discontinued each part of the study. The number and percentage of patients included in each of the analysis populations will be presented. The number of randomized patients in each group will be used as the denominator to calculate percentages. The disposition table will be based on all screened patients.

Patient disposition data listings will be presented.

### 6.2 DEMOGRAPHICS AND BASELINE CHARACTERISTICS

Demographic data as collected on the demographics eCRF page will be summarized. The demographic summary table is expected to present information such as age, race, ethnicity, sex, and other baseline characteristics.

The demographic and baseline characteristics table will be based on the safety set. Patient demographic data listings will be presented.

### 6.3 MEDICAL HISTORY

Medical history will be recorded at screening. Investigators should document the occurrence, signs, and symptoms of the patient's preexisting conditions, including all prior significant illnesses, up to and including 1 year before screening.

#### 6.3.1 Targeted Medical History

A summary table will be shown to present data from the targeted medical history eCRF page. This will include the following.

- Time since diagnosis (missing month and day will be imputed to July 1, missing day only will be imputed to first of the month)
- Diagnostic criteria
- Presence of Symptoms
- Prior hospitalization due to CAD
- Prior hematological malignancy history
- Prior non-malignant hematological disease
- Prior thromboembolic history
- Prior rituximab-based regimen
- Prior transfusions in the 6 months prior to randomization

